### **1.4 Rationale for using Eltrombopag in the Treatment of AML**

To date, there is no effective strategy for managing thrombocytopenia in AML patients following induction chemotherapy (IC) other than supportive platelet transfusions, which are limited by supply, cost and transfusion refractoriness. Eltrombopag is capable of enhancing megakaryopoiesis without stimulating leukemic blasts or activating platelets – properties that make it a candidate drug of choice for therapeutic intervention in the post-induction phase of

AML treatment. Early platelet count recovery following IC has significant clinical implications including decrease in thrombocytopenia-related bleeding complications, reduced necessity for platelet transfusions, improved complete remission rates and timely initiation of post-remission therapy - factors that present challenges particularly in the management of older patients.

While most of the eltrombopag studies in AML are in the relapsed or refractory setting or in those unable to withstand aggressive induction chemotherapy, a phase 1/2 study has been opened to assess the efficacy of eltrombopag in AML patients undergoing consolidation therapy following achievement of CR. We propose a novel therapeutic strategy where eltrombopag will be used in older AML patients undergoing IC who have no morphologic evidence of disease on a day 14 bone marrow assessment, with the goal of accelerating platelet recovery. We hypothesize that as eltrombopag acts at a TPO receptor site which is different from the native TPO binding site, it will accelerate megakaryopoiesis by acting synergistically with endogenous TPO, the levels of which have been shown to rise twenty-fold with drop in platelet counts below 50000/ $\mu$ L in AML patients while undergoing cytotoxic chemotherapy.(27) Our proposed use of eltrombopag in AML-associated thrombocytopenia thus represents a shift in treatment paradigm, with expected benefits in terms of decreased treatment-related morbidity, cost and potentially improved disease outcome. Currently, there are no competing trials in the public domain for this proposed study.

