#### **6.3 Thrombotic/Thromboembolic Complications**

Platelet counts above the normal range present a theoretical risk for thrombotic/thromboembolic complications. In eltrombopag clinical trials in ITP thromboembolic events were observed at low and normal platelet counts. Use caution when administering eltrombopag to patients with known risk factors for thromboembolism (e.g., Factor V Leiden, ATIII deficiency, antiphospholipid syndrome). Platelet counts should be closely monitored and consideration given to reducing the dose or discontinuing eltrombopag treatment if the platelet count exceeds the study target levels. In ITP studies, 21 thromboembolic/thrombotic events were observed in 17 out of 446 subjects (3.8 %). The TEE events included: embolism including pulmonary embolism, deep vein thrombosis, transient ischemic attack, myocardial infarction, ischemic stroke, and suspected PRIND (prolonged reversible ischemic neurologic deficiency). Eltrombopag should not be used in patients with hepatic impairment (Child-Pugh score  $\geq 5$ ) unless the expected benefit outweighs the identified risk of portal venous thrombosis. In 2 controlled studies in thrombocytopenic patients with HCV receiving interferon based therapy, 31 out of 955 subjects (3 %) treated with eltrombopag experienced a TEE (3 %) and 5 out of 484 subjects (1 %) in the placebo group experienced TEEs. Portal vein thrombosis was the most common TEE in both treatment groups (1 % in patients treated with eltrombopag versus < 1 % for placebo). No specific temporal relationship between start of treatment and event of TEE were observed. The majority of TEEs resolved and did not lead to the discontinuation of antiviral therapy. In a controlled study in thrombocytopenic patients with chronic liver disease (n = 288, safety population) undergoing elective invasive procedures, the risk of portal vein thrombosis was increased in patients treated with 75 mg eltrombopag once daily for 14 days. Six of 143 (4 %) adult patients with chronic liver disease receiving eltrombopag experienced thromboembolic events (all of the portal venous system) and two of 145 (1 %) subjects in the placebo group experienced thromboembolic events (one in the portal venous system and one myocardial infarction). Five eltrombopag treated subjects with a TEE experienced the event within 14 days of completing eltrombopag dosing and at a platelet count above 200,000/ $\mu$ l.

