### 7.3 Dose Adjustments for Eltrombopag

If after 2 weeks, the platelet count fails to reach 50,000/ $\mu$  L or above, the dose will be increased to 300 mg orally daily (150 mg orally daily for East-Asians). Depending on tolerability, dose modification will be individualized based on the patient's platelet count response according to the following rules:

Dose Modification / Adjustment of Eltrombopag	
If platelet count is $\leq$ 50,000/ $\mu$ L after 2 weeks of treatment with starting dose of eltrombopag*	Increase daily dose to 150 mg for East-Asians and 300 mg for all other ethnicities
If platelet counts are between 50,000 and $<$ 100,000/ $\mu$ L (untransfused) on the starting or escalated dose of eltrombopag	Continue on the same dose
If platelet counts reach $\geq$ 100,000/ $\mu$ L (untransfused) on the starting or escalated dose of eltrombopag at any time on study	Discontinue eltrombopag

\* Starting dose will be 100 mg for East-Asians and 200 mg for other ethnicities.

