## 7.8 Duration of Follow Up

All study subjects who achieved a platelet count of 100,000/ $\mu$ L will be followed for a total up to 4 weeks from the stop date of eltrombopag or till the start date of post-remission therapy, whichever occurs earlier, for adverse events and response. The patients who are removed from study for unacceptable adverse events will be followed until that adverse event is resolved or stabilized. All patients will thereafter be followed for 5 years from study enrollment for relapse and survival endpoints as part of institutional standard of care policy for all treated AML patients.

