- 9) All study subjects who achieve a platelet count of 100,000/ $\mu$ L will be followed for a total up to 4 weeks from the stop date of eltrombopag or till the start date of post-remission therapy, whichever occurs earlier, for adverse events and response. Adverse events that are related to the study drug (eltrombopag) will be followed through resolution or stabilization. CBCs and CMPs will be collected per standard of care as well as AEs for 4 weeks after stopping eltrombopag or till the start date of post-remission therapy, whichever occurs earlier.

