### Emergency or after-hours contact information

Contact the page operator at [contact] or toll free at [contact], and ask for the oncologist (cancer doctor) that is on call.

The SAE report should comprise a full written summary, detailing relevant aspects of the adverse events in question. Where applicable, information from relevant hospital case records and autopsy reports should be included. Follow-up information should be forwarded to Novartis within 24 hours.

SAEs brought to the attention of the investigator at any time after cessation of eltrombopag and considered by the investigator to be related or possibly related to eltrombopag must be reported to Novartis if and when they occur. Additionally, in order to fulfill international reporting obligations, SAEs that are related to study participation (e.g., procedures, invasive tests, change from existing therapy) or are related to a concurrent medication will be collected and recorded from the time the subject consents to participate in the study until he/she is discharged.

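### Systematic adverse-event collection stops when post-remission therapy starts, with no minimum post-dose period, so thromboembolic events after that date reach the trial only by a passive, judgement-dependent route

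*Combined protocol and SAP*

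**What the plan says.** **Cut-off.** Section 8.2, item 9, ends collection with the words "as well as AEs for 4 weeks after stopping eltrombopag or till the start date of post-remission therapy, whichever occurs earlier". Section 7.8, written for patients who reach 100,000/µL, follows them for up to 4 weeks after stopping or "till the start date of post-remission therapy, whichever occurs earlier, for adverse events and response". Section 11.7 collects AEs and SAEs through a short-term follow-up period, but Section 8.3, which describes that follow-up, gives it no length.

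**Post-remission therapy inside the 4 weeks is expected.** Section 10.1.2 counts a patient at or above 100,000/µL who moves to post-remission therapy within 4 weeks of stopping as a complete response. Section 1.4 lists "timely initiation of post-remission therapy" among the hoped-for benefits of early platelet recovery.

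**The recognised risk.** Section 6.3 reports, from a study of chronic liver disease patients having elective invasive procedures: "Six of 143 (4 %) adult patients with chronic liver disease receiving eltrombopag experienced thromboembolic events". It adds: "Five eltrombopag treated subjects with a TEE experienced the event within 14 days of completing eltrombopag dosing", at platelet counts above 200,000/µL.

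**What remains after the cut-off.** Section 11.7 (under the contact information) requires reporting of "SAEs brought to the attention of the investigator at any time after cessation of eltrombopag" if the investigator considers them related or possibly related. Section 11.2(h) removes serious haematologic events from the SAE definition but keeps unprovoked arterial and venous thromboembolism. Sections 8.2(9) and 11.7 follow drug-related AEs to resolution or stabilisation.

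**The concern.** Section 12 makes safety a primary goal alongside efficacy, and the trial has one arm and at most 31 patients, so each missed event matters. The length of post-dose observation depends on outcome: starting post-remission therapy can shorten it, and patients who never start it cannot be cut short in this way. Thromboembolism is the event for which the protocol itself reports clustering after the last dose.

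The remaining route is passive and needs two judgements. An event must come to the investigator's attention and be called at least possibly related. Thromboembolism also stays an SAE only if unprovoked, and a clot during new chemotherapy could be called provoked. Following known related events to resolution does not find new ones. The 5-year follow-up in Sections 7.8 and 8.4 covers relapse, AML transformation and survival, not thrombosis. The AE table could therefore omit thromboembolic events that occurred soon after the drug was stopped.

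**Working it through.** **1. The plan's own safety figure.** Section 12 states at least an 80% chance of seeing one or more events of 5% risk in 31 patients. Check: 1 − 0.95^31 = 0.796, which agrees to rounding. The figure presumes that every patient is observed throughout the period to which the risk applies.

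**2. How much post-dose time can be lost.** Let S be the day of the last dose and M the day of the remission marrow, both counted from the start of induction. Suppose post-remission therapy starts a fixed lag after the later of the two. Then the observed part of the first 14 post-dose days is min(14, max(M, S) + lag − S). Section 8.3 puts M typically at day 30–45, and Section 10.1.1 gives a historical median time to CR of 34 days. The lag is my assumption.

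| S | M = 34, lag 3 | M = 45, lag 0 |
|---|---|---|
| 20 | 14 | 14 |
| 24 | 13 | 14 |
| 28 | 9 | 14 |
| 32 | 5 | 13 |
| 36 | 3 | 9 |
| 40 | 3 | 5 |

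Truncation is therefore possible. Within each column, an earlier stop gives an equal or longer observed period. If post-remission therapy instead follows the last dose by a fixed L days, the observed period is min(14, L), whatever the speed of recovery.

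**3. Illustrative loss of detection.** Inputs:
- Event rate p = 6/143 = 0.04196 (Section 6.3).
- Five of the six events fall in the 14 post-dose days, assumed evenly spread. The sixth is assumed always captured, since Section 6.3 does not date it.
- Share of patients cut short = 0.41. This borrows the historical CR rate in Section 10.1.1 as a stand-in. That cohort is not described as limited to patients with a clear day-14 marrow, so the true share may differ.

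With d days observed, the captured share of events is f = 1/6 + (5/6)(d/14). The chance of at least one observed event is 1 − (1 − p)^(31 × 0.59) × (1 − pf)^(31 × 0.41).

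Uncut: expected events 31 × 0.04196 = 1.30, and 1 − (1 − 0.04196)^31 = 0.735.

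| d | f | 41% cut short | All 31 cut short |
|---|---|---|---|
| 10 | 0.762 | 0.698 | 0.635 |
| 7 | 0.583 | 0.667 | 0.536 |
| 3 | 0.345 | 0.621 | 0.364 |

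Worked row, d = 3: pf = 0.0145, so 1 − 0.4566 × 0.8307 = 0.621.

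If all six events are placed in the post-dose period instead (f = d/14), the 41% column becomes 0.690, 0.651 and 0.593. For patients who start post-remission therapy after day 14 there is no loss within this model.

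**The case against.** **The cut-off is coherent.** Sections 7.8 and 8.2(9) agree with each other, and AEs up to the next therapy are a legitimate target for a single-arm trial with descriptive safety summaries. Later events are confounded by the new chemotherapy. This stands, and it is why the general rule need not change.

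**A reporting route remains.** Section 11.7 covers possibly related SAEs at any time after the drug is stopped. Under the attribution table in Section 11.1, that category needs only two criteria; timing and a known pattern of response could satisfy it for an early post-dose thrombosis. It would be wrong to infer that late thromboembolism goes wholly unreported. What is lost is systematic collection of events that are not brought forward, or that are called provoked or unrelated.

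**The external study differs.** Its treated-arm events were all in the portal venous system, in chronic liver disease patients. This trial excludes uncontrolled intercurrent illness including cirrhosis, and thrombosis within the past year. Section 7.3 says "Discontinue eltrombopag" once untransfused platelets reach 100,000/µL, whereas five of those events occurred above 200,000/µL. Section 6.3 also notes that ITP events occurred at low and normal counts. A reader might take the 14 days as a monitoring window set by this protocol; it is only a background observation, and 4.2% is a borrowed rate.

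**Faster recovery need not mean less observation.** A reader might infer that the quickest recoverers are watched least. The documents do not support this. Dosing stops at recovery while the remission marrow is dated from induction, so on that timing the relation is flat or runs the other way.

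**Conclusion.** The point holds in a limited form. Routine AE collection has no minimum post-dose period, patients who move to post-remission therapy can be observed for less time than those who never do, and the remaining route for thromboembolism is passive and depends on judgement.

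The size cannot be fixed from the documents, because they do not give the gap from last dose to post-remission therapy. On the borrowed 4.2% rate, with 41% of patients cut short at 3–10 days and events evenly spread, the chance of seeing at least one event falls from about 74% to about 62–70%. The figures of 36–63% with all 31 patients cut short are extremes, not the expected loss. These calculations also count nothing reported through the any-time SAE route, so they overstate the loss to the extent that route works. The primary platelet endpoint is unaffected. This is an inexpensive improvement to safety ascertainment, not a flaw in the main test.

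**What to change.** Keep the current cut-off for general AEs. In Sections 7.8, 8.2(9) and 11.7, add that thromboembolic events are collected by chart abstraction for 4 weeks after the last eltrombopag dose in all treated patients, whether or not post-remission therapy has begun. Tabulate events before and after its start in separate rows, each with the last available platelet count, and report the number of post-dose days observed.

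Separately, reconcile the platelet-count schedule. Section 6.4 calls for daily counts in hospital and then weekly outpatient counts for 4 weeks after discontinuation. Section 8.2(3) and calendar note h end scheduled counts at 100,000/µL, with note h leaving later tests to the treating physician. Section 8.2(9) refers to standard of care until post-remission therapy or 4 weeks. Until these agree, a count before each event is not assured.

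The cost is a wording change and a short abstraction at one institution, with no new visit, test or treatment rule. It is still extra work, because the 5-year follow-up does not collect AEs. The downside is that events after post-remission therapy starts are confounded by it; the separate rows make that visible but do not remove it.

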### **8.3 Short-term Safety Follow-up**

- 1) Bone marrow aspiration and biopsy typically between days 30-45 of IC to assess remission status and thereafter as deemed necessary guided by peripheral counts and or clinical judgment.
- 2) Peripheral blood smear typically between day 30-45 of remission IC at the time of bone marrow biopsy performed to evaluate remission status and at the end of the study period (optional) based on clinical assessment.
- 3) Concurrent medication review (with each clinical assessment)
- 4) CBC with differential and CMP
- 5) Adverse event (AE) monitoring and documentation
- 6) Vital signs and physical exam
- 7) Documentation of all red blood cell and platelet transfusions

### **8.4 Long-term Follow-up**

All participants, regardless of reason for discontinuation, will be followed for survival and for AML transformation (an increase of blasts to a level  $\geq 20\%$  in peripheral blood or bone marrow) for five years from study registration as part of standard of care for CCF leukemia patients.

The following study calendar will be used:

	Pre- induction	Week 1	Week 2	Week 3	Week 4	Week 5	Week 6
						Inpatient/Outpatient	
Induction chemotherapy (IC)							
Study Medicationa							
Informed Consent	X						
Demographicsb	X						
Disease Characteristicsc	X						
Transfusion Historyd	X	X	X	X	X	X	X
Review of concurrent medications	X	X	X	X	X	X	X
Physical Examinatione	X	X	X	X	X	X	X
CSBEf	X	X	X	X	X	X	X
Performance statusg	X						
Hematologyh	X	X	X	X	X	X	X
Serum Biochemistryi	X	X	X	X	X	X	X
Chest x-ray	X						
Peripheral Blood Smearj	X					X	
Bone marrow biopsyk	X		D14 - 17			X	
Ophthalmology examl	X						
12 lead ECG	X			X m			
Adverse event monitoringn				X	X	X	X

Pre-induction assessment refers to evaluation at the time of diagnosis of AML prior to start of remission induction chemotherapy. Weeks as enumerated in the table refer to the time from the start date (day 1) of remission induction chemotherapy.

Week 1 is the week when the patient receives the standard 7+ 3 (cytarabine and anthracycline) remission induction chemotherapy

a. **Study Medication:** Eltrombopag dose as assigned. The drug will be started within 5 business days from the date of day 14 bone marrow biopsy if the day 14 bone marrow biopsy (range, 14-17) shows no morphological evidence of leukemia and will be continued for a total of 4 weeks unless discontinued earlier for reasons stated in the protocol.

b. **Demographics:** Date of birth, race, ethnicity, and gender.

c. **Disease Characteristics:** Date of AML diagnosis, AML category as classified by WHO, primary vs. secondary AML, type of secondary AML (antecedent hematologic disorder, therapy-related including prior radiation therapy and or cytotoxic chemotherapy for any condition).

d. **Transfusion History:** Transfusion requirements of red blood cells and platelets up to 8 weeks prior to the diagnosis of AML and during hospital stay.

e. **Physical Examination:** Weight, height (during screening only), body temperature (oral), blood pressure, pulse rate, respiratory rate and pulse oximetry (oxygen saturation).

f. **CSBE:** Clinically Significant Bleeding Events includes hematuria, gastrointestinal bleed, retroperitoneal bleeding, intra-cranial bleed, epistaxis not controlled by conservative measures and muscle or soft tissue hematomas. CSBE will not include petechial skin rash, ecchymosis or mucosal petechiae.

g. **Performance Status** as per ECOG scale.

h. **Hematology:** CBC with differential will be monitored daily during hospital stay. Once the patient is discharged, CBC with differential will be checked within 72 hours, thereafter CBC with differential will be checked weekly until the subject's platelets reach 100,000/ $\mu$ L. Once the platelet counts reach 100,000/ $\mu$ L, the labs will be done at the discretion of treating physician as part of routine standard of care.

i. **Serum Biochemistry:** Complete metabolic panel (CMP) will be checked daily during hospital stay. CMP will include albumin, total protein, alkaline phosphatase, total bilirubin, SGOT[AST], SGPT[ALT], sodium, potassium, chloride, bicarbonate, BUN, creatinine, glucose, and calcium. Magnesium and phosphorus will be resulted if clinically indicated. Once the patient is discharged, CMP will be checked weekly until the subject's platelets reach 100,000/ $\mu$ L. Once the platelet counts reach 100,000/ $\mu$ L, the labs will be done at the discretion of treating physician as part of routine standard of care. ELISA for HIV and remote hepatitis panel will be checked only once at the time of study screening (pre-induction).

j. **Peripheral Blood Smear:** Will be performed prior to start of induction chemotherapy, typically between day 30 and 45 of induction chemotherapy while checking for remission status, and at the end of the study period (optional) based on clinical assessment.

k. **Bone marrow biopsy:** Bone marrow evaluation will include cellularity analysis, morphological assessment of all three cell lineages, assessment of blast percentage, fibrosis and metaphase cytogenetics. Tests for molecular mutations and FISH studies will be done as necessary as part of standard of care where indicated. **D14-17** denotes marrow evaluation between day 14 to 17 from the start date of IC to check for persistent disease. **D30-45** denotes marrow evaluation typically between day 30 to 45 from the start date of IC to check for remission status or refractory disease. The need for additional bone marrow biopsies including end of study bone marrow biopsy will be determined clinically based on peripheral blood count abnormalities or morphology

l: **Ophthalmologic evaluation:** Complaints of any new or recent onset visual symptoms at the time of AML diagnosis. Those with known prior or existing ocular conditions such as any vitreoretinal diseases, age-related macular degeneration, optic nerve disease, glaucoma and corneal diseases as well as patients in whom there is clinical suspicion of cataracts will be evaluated at baseline. A follow up exam will be done at 2 months after stopping the drug if clinically indicated.

m: A 12-lead ECG will be obtained for each patient at screening (baseline). A pre- and post-dose 12-lead ECG will be performed on the first day of eltrombopag administration. The post-dose ECG is to be performed within a 2-4 hour window post-dose (preferably within 3 hours after administration of study drug). Thereafter, 12 lead ECGs will be performed as clinically indicated.

n: Adverse events that are related to the study drug (eltrombopag) will be followed through resolution or stabilization.

